9.5. Reporting procedure for all AE

All local and systemic AEs occurring in the 28 days following each vaccination observed by the Investigator or reported by the participants, whether or not attributed to study medication, will be recorded. Recording and reporting of all AEs will be detailed in SOP. All AEs that result in a participant withdrawal from the study will be followed up until a satisfactory resolution occurs or until a non-study related causality is assigned (if the participant consents to this). SAEs will be collected throughout the entire trial period (i.e. until W24).

SAEs will be reported on the SAE forms by doctors who enrolled participants to the principal investigator and DSMB. SAE will be documented accurately and notified within 48 hours to the DSMB. The DSMB will also review severity and causality analysis within 2 days and will provide advice on study continuation. AEs will be reported to DSMB within 7 days. In special circumstance the chair of DSMB may decide to involve the ethical committee to analyze AE reports in order to define how to continue the study.

SAR and SUSAR that occur within week 10 of the study will determine a temporal suspension of the enrollment pending the decision of DSMB. The suspension is decided by the local investigator and immediately communicated to principal investigator and DSMB. When a SAR or a SUSAR occurs among participants enrolled in a clinical center the investigator of the clinical center will immediately contact the principal investigator who will eventually contact other enrolling centers.

9.6. Assessing severity of adverse events

The severity of the adverse events will be assessed according to the scale reported below. In particular AE will be judged according to inspection of injection area, medical visit and review of all biochemical and hematological tests carried out at each endpoint. AEs autonomously reported by participants outside medical visit will be immediately evaluated by investigators on a telephone interview. Investigators may decide to admit participant to hospital for further investigation if needed.

9.7. Management of participants with AE

The clinical center that enroll participants will provide care to any participant with any AE as appropriate for the clinical conditions.

Each enrolling center will have a medical investigator that will ensure real-time safety oversight. The local medical investigator will review AEs deemed possibly, probably or definitely related to study interventions. The local investigator will immediately register AE and will notify them to principal investigator according to SOP. Moreover the local investigator can decide to place the study on hold if deemed necessary following a study intervention-related as severe or unexpected event such as: SAE, UAR, SAR and SUSAR. The decision to put the study on hold is immediately notified to principal investigator and to DSMB.

Table 1 Adverse event severity scale

Adverse events	Severity			
	None	Mild	Moderate	Severe
Erythema	no	3-50 mm	51-100 mm	>100 mm
Swelling	no	3-20 mm	21-50 mm	> 50 mm
Ulceration	-	-	-	any
Fever	36.0-37.4	37.5-38.0	38.1-39.0	>39.0
hypothermia		35.9-35.1	-	<35
Tachycardia (bpm)	55-100	101-115	116-130	>130
bradycardia (bpm)		50-54	40-49	≤40
Systolic hypertension	85-140	141-159	160-179	>179
Systolic hypertension		85-89	80-84	<80
Diastolic hypertension	<90	91-99	100-109	>109
Respiratory Rate low	12-20	-	9-11	<9
Respiratory Rate high		-	21-24	>24
SpO2 at FiO2 21%	>97	94-96	92-93	<92
Consciousness	Alert	-	-	any
Biochemistry	MedDra and CTAE. Grade 1-2=mild; Grade 3/4= severe/life threatening			
Blood counts				

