#### 4.11.1 Adverse Events

Adverse events (AEs) will be coded using the Medical Dictionary for Regulatory Activities (MedDRA) Version 23.0.

An AE is any untoward medical occurrence in a study subject administered an IMP which does not necessarily have a causal relationship with this treatment. An AE can therefore be any unfavorable and unintended sign (including a clinically significant abnormal laboratory finding), symptom, or disease temporally associated with the use of an IMP, whether or not considered related to the IMP. Adverse events may include the onset of new illness and the exacerbation of pre-existing conditions.

Other untoward events occurring in the framework of a clinical study will be recorded as AEs, e.g. those occurring during treatment-free periods (including Screening or post-treatment Follow-up periods), in association with study-related procedures and assessments or under placebo.

Concomitant illnesses, which existed before entry into the clinical study, will not be considered AEs unless they worsen during the treatment period. Pre-existing conditions will be recorded as part of the subject's medical history.

A treatment-emergent adverse event (TEAE) is defined as an AE that begins or worsens in severity in 28 days after study drug administration.

Adverse event with 'No Relationship' or 'Unlikely Related' causality will be evaluated as not related (relationship = No), otherwise (including missing causality) AE will be evaluated as related (relationship = Yes).

Adverse events with completely unknown start dates will be considered as treatment-emergent for the tabulations and will be shown as NK in the listings. Partially complete AE dates will not be imputed in the listings and the available day, month and year components will be used to determine if an adverse event is treatment-emergent taking the first dosing date and end of study date as references.

Solicited adverse reactions are foreseeable AEs following vaccination with GRAd-COV2 including the following AEs: injection site pain, erythema, warmth, swelling, pruritus, myalgia, arthralgia, headache, fatigue, fever, feverishness, malaise and nausea. Solicited adverse reaction is recorded as such on the corresponding AE's eCRF.

Adverse events of special interest (AESI) are any grade  $\geq 3$  abnormalities on safety blood test according to Common Terminology Criteria for Adverse Events v.5.0 (CTCAE, see section [4.11.3](#)).

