An overview will be provided with the number and percentage of subjects as well as the total number of occurrences of the following event categories by treatment group:

- Any TEAE;
- Any TEAE related to study drug;
- Any treatment-emergent SAE (see section [4.11.2](#));
- Any treatment-emergent SAE related to study drug;
- Any TEAE leading to study discontinuation;
- Any AESI;
- Any solicited adverse reactions emerged in the first 7 days post dose.

Adverse event summaries by system organ class (SOC) and preferred term (PT) with number and percentage of subjects as well as the total number of occurrences will be provided by treatment group for the following:

- All TEAE;
- TEAEs by maximum severity;
- TEAEs by causality;
- All AESI;
- All solicited adverse reactions emerged in the first 7 days post dose.

Additional summary for all TEAE will be provided by PT and treatment group.

Adverse event summaries will be ordered in terms of decreasing frequency for SOC and PT within SOC in the Total group and then alphabetically for SOC and PT within SOC. Summaries will be ordered in terms of decreasing frequency for PT in the Total group in summaries where SOC is not included.

For each subject and each adverse event, the worst severity recorded will be attributed and used in the by-severity summaries. Similarly, the worst causality (most related to treatment) will be attributed and used in the by-causality summaries. If severity or causality is missing, a conservative approach for AE assessment (taking into account the worst case) will be followed.

By-subject listing of all adverse events (including non-treatment-emergent events) will be provided by treatment group. Adverse event listing will include center, subject identifier, age, sex, race, adverse event (SOC, PT, and verbatim term), date of onset, date of resolution, duration, solicitation flag, special interest flag, severity, seriousness, action taken, outcome and causality.

Adverse event listings will be provided for the following:

- All AEs
- All severe TEAE;
- All TEAE related to study drug;
- All AESI;
- All solicited adverse reactions emerged in the first 7 days post dose.

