#### 4.11.3 Clinical Laboratory Evaluation

Safety laboratory evaluations (hematology, biochemistry and urinalysis) will be assessed as shown in the Schedule of Assessments (Appendix 6.1). For list of safety laboratory test parameters refer to Blood test and other analysis for monitoring safety (section 8.3) in study protocol.

Urinalysis results will be listed only.

Hematology and biochemistry results will be graded according to NCI CTCAE (Version 5.0). Individual CTCAE grades will be provided with the by-subject listings.

For each hematology and biochemistry parameter:

- Results and change from baseline will be summarized descriptively by visit and treatment group;
- Number and percentage of subject in normal range categories will be tabulated by visit and treatment groups.
- Number and percentage of subject in each CTCAE severity grades will be tabulated by visit (and overall) and treatment groups.

Worst post-baseline record will be selected (flagged) by utilizing the rules as follow:

If there is any LOW or HIGH record, flag the most extreme record. Most extreme record will be derived by using the factor (f) for corresponding normal limits as appropriate ( $f \times LLN$  or  $f \times ULN$ ). If there are multiple records with most extreme value, flag the earliest occurrence. If not out of normal range results is observed flag the first post-baseline observation.

By-subject listing of hematology and biochemistry with change from baseline will be provided by dose and time point for each treatment group separately.

All values outside the clinical reference ranges will be flagged in the data listings. The abnormal values will be flagged with 'L' for values below the lower limit of the clinical reference range and 'H' for values above the upper limit of the clinical reference range and included in the listings. The Investigator will assess whether the values outside the clinical reference range are clinically

significant (CS) and these will be reported as abnormal NCS or abnormal CS. Clinically significant laboratory values will be recorded by the Investigator as AEs.

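### Protocol Table 1 gives laboratory adverse events no moderate level, so grade 2 laboratory TEAEs are pooled with grade 1 as mild in the by-severity table

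*Protocol*

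**What the plan says.** Protocol 9.6 states: "The severity of the adverse events will be assessed according to the scale reported below". It adds that the judgement draws on the injection site, the medical visit and the biochemical and haematological tests. The scale is Table 1, printed under Protocol 9.7. For biochemistry and blood counts it refers to MedDRA and CTCAE and sets the levels as "Grade 1-2=mild; Grade 3/4= severe/life threatening".

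SAP 4.11.1 lists "TEAEs by maximum severity" among the summaries by system organ class and preferred term, and says how severity enters: "For each subject and each adverse event, the worst severity recorded will be attributed and used in the by-severity summaries". On which events qualify: "A treatment-emergent adverse event (TEAE) is defined as an AE that begins or worsens in severity in 28 days after study drug administration".

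SAP 4.11.3 decides which laboratory results become events: "Clinically significant laboratory values will be recorded by the Investigator as AEs". Separately, it plans a table of the results themselves: "Number and percentage of subject in each CTCAE severity grades will be tabulated by visit (and overall) and treatment groups". The SAP neither restates nor changes the laboratory mapping in Table 1.

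**The concern.** Protocol 10.2 presents safety by frequency, severity and duration, and safety is the primary objective. A by-severity table is read on the understanding that one level means roughly the same thing in every row. Here most clinical rows use three levels of abnormality, and the laboratory rows use two. A reader comparing doses would see grade 2 laboratory events mixed with grade 1 under mild, with nothing on the page to say so.

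Laboratory safety was a live question in this trial. SAP 4.15 adds liver-enzyme analyses after a DSMB meeting in October 2020. The interim reports described in SAP section 1 are meant to inform the choice of dose for a later trial.

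**Working it through.** No figure in the plan can be reproduced on this point, and no sample size, error rate or expected event rate is tied to it. The check traces a laboratory result through the two documents.

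**Step 1: the mapping.** Inputs: Protocol Table 1 and SAP 4.11.3.

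| CTCAE grade | Level in Table 1 | Level if each grade is kept apart | SAP laboratory table |
|---|---|---|---|
| 1 | Mild | Mild | Grade 1 |
| 2 | Mild | Moderate | Grade 2 |
| 3 | Severe | Severe | Grade 3 |
| 4 | Severe/life threatening | Severe/life threatening | Grade 4 |

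No grade falls in the Moderate column. Only the grade 2 row differs between the second and third columns. For comparison, a fever of 38.5 °C lies in the 38.1–39.0 band of Table 1, which is moderate; SAP Table 4 agrees.

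**Step 2: which events are affected.** A grade 2 result is counted as mild in the TEAE table only if all of these hold:
- the investigator judged it clinically significant (SAP 4.11.3);
- it began or worsened within 28 days (SAP 4.11.1);
- grade 2 was the worst level of that event;
- the site graded it by Table 1, since the SAP uses the recorded severity and does not cite the table.

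Safety bloods are taken at seven visits after vaccination: D2, W1, W2, W4, W8, W12 and W24. Three of these (W8, W12, W24) fall after 28 days. W4 has a window of ±2 days, so a late W4 sample can also miss.

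**Step 3: the worsening clause.** A laboratory AE that begins after vaccination and within 28 days is a TEAE whatever its level. One already present at vaccination qualifies only if its severity rises. If severity follows Table 1, a move from grade 1 to grade 2 is mild to mild and need not count as worsening. For these events the pooling can affect inclusion as well as the label. Inclusion criterion 12 (Protocol 6.4), which bars laboratory abnormalities of possible clinical significance, should make this uncommon.

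**Step 4: size.** The number of affected participants, k, is not in the documents. The shift in an arm of 15 is 100 × k/15 points:
- k = 0: 0
- k = 1: 6.7
- k = 2: 13.3
- k = 3: 20.0

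These values of k are illustrations only. In a cohort total of 45, one participant is 100/45 = 2.2 points. At preferred-term level the shift is from mild to moderate in that row. In any count of participants by their worst event overall, it appears only if the participant has no other event of moderate or higher severity.

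**Step 5: decisions.** The laboratory criterion for an SAE in Protocol 9.1 starts at grade 3, as does the AESI definition in SAP 4.11.1. Halting rules A and B (Protocol 9.8) concern severe solicited events, C and D serious events, E life-threatening conditions and F death. None depends on whether grade 2 is called mild or moderate.

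**The case against.** The strongest case against is that this is an openly stated, protocol-specific scale and that nothing is lost. Much of that stands.

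- A reader might infer that every grade 2 laboratory adverse event is understated. The documents do not support this. The conditions in step 2 exclude many grade 2 results, and neither document says that CTCAE grade 2 means moderate. What they support is that the laboratory rows are coarser than most others and not comparable with them.
- A reader might infer that a dose-related grade 2 signal would be hidden. It would not. SAP 4.11.3 gives each CTCAE grade by visit, overall and by arm, with change from baseline and listings, and SAP 4.11.4 adds liver categories and an eDISH plot. Those tables count results, however, not events with causality, so they do not replace the TEAE table.
- A reader might say that the two SAP tables contradict each other. They count different things and need not agree under any mapping.
- Other rows of Table 1 also skip levels: ulceration, hypothermia and consciousness have no moderate band, and respiratory rate has no mild band. That is correct. Those gaps are marked with a dash, while the laboratory row joins two grades and gives no reason.
- A share of participants with at least moderate TEAEs is not a planned output, and SAP 4.13 plans no formal tests. A reader would have to derive that share.
- The SAP cites Protocol Version 2.0, places the laboratory tests in section 8.3 (7.3 in the protocol supplied) and shows a screening window of 28 days in the body of its schedule against 21 days in the protocol. The supplied Table 1 may not be the version in force when the SAP was written.

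**Conclusion.** A limited point holds. Under the plan as written, a laboratory TEAE whose worst grade is 2 is pooled with grade 1 as mild and is not on the same footing as the other events in the by-severity table. A laboratory AE already present at vaccination that rises from grade 1 to grade 2 may also not register as worsening.

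This rests on sites having graded laboratory events by Table 1 and on the supplied table being the operative one. The number of events cannot be calculated and could be zero. Grade 2 results remain visible elsewhere, severe counts do not change, and no participant-safety rule is affected. It is a cheap improvement in reporting and no obstacle to interpreting the trial.

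**What to change.** In Table 1, give laboratory grade 2 its own level: grade 1 mild, grade 2 moderate, grade 3 severe, grade 4 severe/life threatening. State the same mapping in SAP 4.11.1.

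For data already recorded, keep the investigator's severity and do not overwrite it. Add a summary of laboratory TEAEs by CTCAE grade and arm, and a footnote to the by-severity table explaining how laboratory events were graded. Use one CTCAE version throughout: Protocol 9.1 cites v.4 and SAP 4.11.1 and 4.11.3 cite 5.0, and these must be reconciled first.

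The cost is one protocol table row, a short SAP addition and some programming to link each laboratory AE to its graded result, a link the SAP does not now describe. The count of moderate events may look slightly less favourable. Nothing new needs to be collected, and the grade 3 thresholds stay as they are.

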9.8. Halting rules and study termination due to safety issue

Safety halting rules have been developed considering the fact that this is a *first-in-human* dose escalation study. Solicited adverse events are those listed as in section 9.2, occurring within the first 7 days after vaccination (day of vaccination and six subsequent days). Unsolicited adverse events are AE other than the solicited AEs occurring within the first 7 days, or any AEs occurring after the first 7 days after vaccination.

Enrolment of participants in one arm will be upheld if:

- A. Solicited local adverse events (site of injection): 2 or more vaccinations in a group are followed by the same severe solicited local adverse event beginning within 2 days after vaccination (day of

vaccination and one subsequent day) and persisting at severe for >48 hrs and these are deemed possibly, probably or definitely related to study interventions.

- B. Solicited systemic adverse events: If 2 or more vaccinations in a group are followed by the same severe solicited systemic adverse event beginning within 2 days after vaccination (day of vaccination and one subsequent day) and these are deemed possibly, probably or definitely related to study interventions.
- C. Unsolicited adverse events: If 2 or more vaccinations in a group are followed by the same serious unsolicited adverse event (including the same laboratory adverse event) and relation with vaccination cannot be immediately excluded.
- D. One participant with serious adverse event considered possibly, probably or definitely related to vaccination occurs
- E. Life-threatening condition when relation with study intervention cannot be immediately excluded.
- F. Death when relation with study intervention cannot be immediately excluded.

If a halting rule has been met, we will inform the regulatory authority. Moreover, before restarting enrollment the DSMB should exclude that AE has no immediate causal relation with the vaccine or that benefit of vaccination outweigh risk of further AE occurrence. In these latter case Ethical committee should be involved in the decision. Halting rules apply to one dose and the next higher one, so that if halting rule is met for the highest dose, only this arm is upheld. If halting is met for intermediate dose, two arms are held. If halting rule is met for the lowest dose all the study is stopped pending on the investigation of causal association between AE and vaccination (DSMB advice).

The DSMB will always consider:

- A. The relationship of the AE or SAE to the vaccine.
- B. The relationship of the AE or SAE to the vaccine dose, or other possible causes of the event.
- C. If appropriate, additional screening or laboratory testing for other participants to identify those who may develop similar symptoms and alterations to the current Participant Information Sheet are discussed.
- D. New, relevant safety information from ongoing research programs on the various components of the vaccine.

The day of vaccination participants should have no evidence of clinical condition that may resemble AE.

10. Statistical plan

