Figure 7 Estimated time (week) for enrollment and follow-up for Elderlies-Cohort. Figures within cells represent time (in weeks) after vaccination Grey bars represent timing of authorization for enrollment. Blue cells represent time of participants' enrollment. Emerald green cells represent time for safety assessment. Golden cells represent time of sampling carried out for immunogenicity assay on frozen specimens Red cells represent time of sampling carried out for immunogenicity assay on fresh samples. Orange cells represent milestones (letters represent the specific milestone). Olive green cells represent deliverables (numbers represent the specific deliverable).

5. Study design

This is a *first-in-human*, open-label, dose escalation, phase 1A/1B clinical trial to assess the safety and immunogenicity of the candidate GRAd-COV2 vaccine in healthy volunteers aged 18-55 years and elderly volunteers aged 65-85 years. The vaccine will be administered intramuscularly once in time.

We aim to enroll 90 patients in two cohorts with three arms each (i.e. 15 participants per arm in six arms). Each of the study arm will assess a unique dose of the candidate GRAd-COV2 in a particular population, either adults or elderlys.

- Adults-Cohort (Phase 1A):
 - Arm-1 will investigate safety and immunogenicity of a dose of 5×10^{10} viral particles in adults.
 - Arm-2 will investigate safety and immunogenicity of a dose of 1×10^{11} viral particles in adults.
 - Arm-3 will investigate safety and immunogenicity of a dose of 2×10^{11} viral particles in adults.
- Elderlies-Cohort (Phase 1B)
 - Arm-4 will investigate safety and immunogenicity of a dose of 5×10^{10} viral particles in elderlys.
 - Arm-5 will investigate safety and immunogenicity of a dose of 1×10^{11} viral particles in elderlys.
 - Arm-6 will investigate safety and immunogenicity of a dose of 2×10^{11} viral particles in elderlys.

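### Protocol 9.8 contradicts itself on restart and on which arms a halt covers, and does not say whether a halt in one age cohort reaches the other

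*Protocol*

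**What the plan says.** Protocol section 9.8 lists six triggers (A to F) under the lead-in "Enrolment of participants in one arm will be upheld if". It then makes four statements about scope:

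- General rule: "Halting rules apply to one dose and the next higher one".
- Highest dose: "if halting rule is met for the highest dose, only this arm is upheld".
- Intermediate dose: "If halting is met for intermediate dose, two arms are held".
- Lowest dose: "If halting rule is met for the lowest dose all the study is stopped", pending investigation of causality.

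On restart it says: "before restarting enrollment the DSMB should exclude that AE has no immediate causal relation with the vaccine". The alternative, that benefit outweighs further risk, hangs on the same verb, and in that case the ethics committee is to be involved.

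Other places bear on the same event. Section 5 suspends enrolment after a serious event within 48 hours of injection until a direct vaccine effect has been ruled out. Section 9.5 suspends enrolment, with no limit by arm, for a serious adverse reaction up to week 10 of the study. Section 13.1 says enrolment is withheld when a halting rule is met and that the DSMB gives binding advice on restart. The design is "15 participants per arm in six arms" (section 5). Section 7.1 assigns the lowest dose to Arms 1 and 4, the intermediate to Arms 2 and 5, and the highest to Arms 3 and 6.

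**The concern.** This is the operative stopping rule of a first-in-human dose escalation. Two sites, the principal investigator and the DSMB must act on it quickly after a serious event, and should reach the same answer from the text. Two things they need are not given consistently: which arms stop, and what must be established before enrolment resumes.

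The scope question has practical weight because the elderly cohort opens while adults are still in follow-up. If a related serious event appears late in an adult arm, section 9.8 does not say whether the elderly arms at the same or a higher dose are held.

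**Working it through.** **Inputs.** Six arms of 15: 6 × 15 = 90, which reproduces the planned total. There are three doses and two cohorts, so two arms per dose. The stated scope for highest / intermediate / lowest is 1 arm / 2 arms / whole study, that is 1 / 2 / 6.

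**Step 1: does any one rule return the stated scope?** Arms held = dose levels caught × cohorts caught. The dose plus the next higher one catches 1 / 2 / 2 levels; the dose plus all higher ones catches 1 / 2 / 3.

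| Reading | Highest | Intermediate | Lowest |
|---|---|---|---|
| Lead-in: one arm | 1 | 1 | 1 |
| Dose + next higher, one cohort | 1 | 2 | 2 |
| Dose + next higher, both cohorts | 2 | 4 | 4 |
| Dose + all higher, one cohort | 1 | 2 | 3 |
| Dose + all higher, both cohorts | 2 | 4 | 6 |
| **Stated in 9.8** | **1** | **2** | **6** |

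No row matches. The one-cohort readings give the first two entries (Arm 3 or 6; Arms 2 and 3, or 5 and 6) but not the third. The only reading that gives 6 for the lowest dose gives 2 and 4 for the others.

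**Step 2: size, in planned participants (15 per arm).**

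- Highest dose: 1 × 15 = 15 within cohort, or 2 × 15 = 30 across cohorts.
- Intermediate dose: 2 × 15 = 30, or 4 × 15 = 60.
- Lowest dose: the general sentence gives 30 within one cohort or 60 across both; the specific sentence gives 6 × 15 = 90.

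**Step 3: restart.** Let R mean that the event is caused by the vaccine. Section 5 lifts the suspension once R is excluded. Section 9.8 literally asks the DSMB to exclude not-R, which amounts to establishing R. On the same grammar, its second branch asks the DSMB to exclude that benefit outweighs risk. The two sections therefore point in opposite directions.

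**Step 4: can the cross-cohort case arise?** Triggers A and B concern events that begin within 2 days. Triggers D to F (related serious event, life-threatening condition, death) have no time window, and section 9.5 collects serious events to week 24. Figures 6 and 7 are not available, so the following calendar is an assumption: one week per enrolment block, one week per 7-day review, no delays, and study weeks counted from the first vaccination.

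- Adult blocks fall in weeks 1, 3, 5 and 7 (Arm 1A; 1B with 2A; 2B with 3A; 3B).
- Arm 1B is vaccinated in week 3, so its 4-week data arrive in week 3 + 4 = 7, and Arm 4A opens in about week 8.
- The remaining elderly blocks fall in weeks 10, 12 and 14 (4B with 5A; 5B with 6A; 6B).
- The first adult stays in follow-up until week 1 + 24 = 25, so all adults are still under observation throughout elderly enrolment.
- The automatic suspension in section 9.5 ends at week 10. The blocks in weeks 12 and 14, with 12 + 3 + 12 = 27 elderly participants, fall after it.

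On this calendar, a related serious event in Arm 2 in week 11 holds Arms 2 and 3 if read within cohort, both already enrolled. Read by dose, it also holds Arms 5 and 6.

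**The case against.** A reader might infer that section 9.8 tells sites to keep enrolling after a halting event, because *upheld* means maintained. The documents do not support that. The section is titled as halting rules, speaks of restarting, and uses held and stopped for the other doses; section 13.1 says withheld. This is a language slip with no live alternative reading.

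A reader might also infer that which arms stop is wholly undefined. That is too strong. The lowest-dose outcome is explicit, and a specific sentence can be read as an exception to the general one. The counts of one and two arms fit a within-cohort reading.

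On restart, section 5 states the direction clearly for early serious events, section 13.1 leaves restart to binding DSMB advice, and the ethics committee clause makes sense only under the evident intention. Most readers would recover it.

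The cross-cohort gap is also narrow. The cohorts enrol in sequence, so by the time of an elderly-arm event there would usually be little or no adult enrolment left to hold. No elderly group opens without a DSMB decision, the DSMB meets weekly during enrolment, serious events reach it within 48 hours, and local investigators can place the study on hold (section 9.7). Figure 8 is not shown and the DSMB charter cited in the SAP was not available; either may state the scope.

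All of this limits the likely harm. It does not make the sentences of 9.8 consistent, and the late adult event during elderly enrolment remains unaddressed. Section 13.1 does not name the arms, and the SAP (sections 3.1 and 4.11.7) repeats the authorisation sequence without any halting scope.

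**Conclusion.** Wrong as written. Three things stand, in descending order of weight:

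1. **Scope.** The general rule, the lowest-dose sentence and the single arm of the lead-in conflict, and cohort scope is not stated. An intermediate-dose event holds 2 or 4 arms, and a highest-dose event 1 or 2, depending on an unstated choice.
2. **Restart.** The condition is literally the reverse of that in section 5.
3. **Verb.** *Upheld* is a wording slip only.

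Participant figures use planned arm sizes, not numbers still to be enrolled when an event occurs. The 27 elderly participants in step 4 rest on the assumed calendar; the gap itself needs only that adults are still in follow-up while elderly arms enrol. The finding concerns the protocol text and makes no claim about what the DSMB charter may contain. Which scope or restart rule is clinically right is not judged here.

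**What to change.** Reconcile section 9.8 with sections 5, 9.5 and 13.1:

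- Use one verb for suspension throughout.
- Restate the restart condition, including the benefit–risk branch, so that its literal meaning is the intended one and agrees with section 5 or states why it differs.
- Add a six-by-six table showing, for an event in each arm, which arms are held. State the cohort scope explicitly and remove or qualify the lead-in's single arm.
- Say how the suspensions in sections 5 and 9.5 relate to 9.8 when the same event meets more than one of them.

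The sponsor and DSMB decide the content, and the DSMB charter should be checked against it. The cost is a few sentences and a small table in a protocol amendment; sample size, visits and analyses do not change.
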